Preliminary efficacy and safety data from a phase II study, led by Martha Lacy, et al, at Mayo Clinic, were published. Sixty patients with relapsed or refractory multiple myeloma were enrolled. Pomalidomide (CC-4047) was given orally at a dose of 2 mg daily on days 1-28 of a 28-day cycle and dexamethasone was given orally at a dose of 40 mg daily on days 1, 8, 15, 22 of each cycle. Patient also received aspirin 325 mg once daily for thromboprophylaxis. The study endpoints were the response rate in patients taking pomalidomide plus dexamethasone including patients with lenalidomide resistant refractory multiple myeloma, and safety of pomalidomide plus dexamethasone. Responses were recorded using the criteria of the International Myeloma Working Group. Thirty eight patients achieved objective response (63%) including CR in 3 patients (5%), VGPR in 17 patients (28%), and PR in 18 patients (30%). The CR + VGPR rate was 33%. Grade 3 or 4 hematologic toxicity occurred in 23 patients (38%); and consisted of anemia in three patients (5%), thrombocytopenia in two patients (3%) and neutropenia in 21 (35%). Among those that developed grade 3/4 neutropenia, all first experienced the neutropenia in cycle 1-3; no new patients experienced grade 3/4 neutropenia in cycle 4 or later. The most common non-hematological grade 3/4 toxicities were fatigue (17%) and pneumonia (8%). Other grade 3/4 non-hematological toxicities that occurred in less than 5% included diarrhea, constipation, hyperglycemia, and neuropathy. One patient (1.6%) had a thromboembolic event of deep vein thrombosis. Lacy et al. have also demonstrated promising clinical activity of pomalidomide in myeloma patients with persistent disease following lenalidomide treatment.

CC-4047-MM-002 is a Celgene sponsored phase 1b/2 multi-center, randomized, open-label, dose escalation study that is evaluating the safety and efficacy of oral

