4.0 Study Calendars

4.1 Test Schedule (excluding routine investigations in the peri-ASCT period*)

Tests and procedures	Prior to Registration		Induction and consolidation ^{16,1}	Every cycle pre-treatment including maintenance ^{1,7}	End of Cycle 4 of induction, post ASCT between Day 60-120, end of consolidation and 1 year post initiation of maintenance ^{1,14}	End of Treatment (±14 days) ¹
	≤30 days	≤14 days				
Complete medical history	X				X	
Adverse Event monitoring		X		X	X	X
Physical exam, including weight and vital signs		X		X	X	X
Height		X			X	
Performance status (ECOG scale)		X		X	X	X
Serum pregnancy test		X ¹¹				
CBC with differential		X	X ¹⁵	X ¹⁵	X	X
Chemistry group: sodium, potassium, glucose, alkaline phosphatase; total and direct bilirubin; SGOT (AST); SGPT (ALT), serum creatinine, calcium		X		X	X	X
HIV, hepatitis B and C	X					
LDH, Beta ₂ -microglobulin, C-reactive protein	X				X	
Electrophoresis of serum and urine (SPEP/UPEP)		X		X ³	X	X ³
Affected immunoglobulin ²		X		X ²	X	X ²
Immunofixation serum and urine	X			X ⁴	X	X ⁴
Immunoglobulin free light chain (MML panel)		X		X ⁵	X	X ⁵
ECG	X					
X-ray skeletal survey or whole-body low-dose CT	X			X ⁶	X ⁶	X
CT Scan, PET/CT, or MRI for measurement if evidence of prior EMD lesion ⁸	X			X ⁸	X ⁸	
Circulating plasma cell assessment (flow cytometry or peripheral smear) ⁹		X		X ⁹	X ⁹	
Bone marrow aspirate and biopsy for myeloma ¹⁷	X			X ¹⁰	X ¹⁰	X

Tests and procedures	Prior to Registration		Induction and consolidation ^{16,1}	Every cycle pre-treatment including maintenance ^{1,7}	End of Cycle 4 of induction, post ASCT between Day 60-120, end of consolidation and 1 year post initiation of maintenance ^{1,14}	End of Treatment (± 14 days) ¹
	≤ 30 days	≤ 14 days				
Chest x-ray	X					
Register patient for POMALYST REMS TM program		X ¹²				
Patient Medication Diary (Appendix II) ¹³				X	X	X
Mandatory Research Bone marrow sample ¹⁸	X ¹⁴				X ¹⁴	

*Performed per institutional guidelines. Melphalan conditioning followed by stem cell infusion is being considered as ‘cycle 5’ in the protocol for logistical reasons only. No additional toxicity data will be collected in the immediate post ASCT period until day 60-100 when the patient returns for routine post-ASCT reevaluation.

- 1) All scheduled visits are while patient is receiving therapy will have a window of ± 7 days unless otherwise stated.

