- 14) At baseline, end of the phase induction, ~ Day 100 post ASCT, end of consolidation, and 1 year after initiation of maintenance while on maintenance. See [Section 14.0](#).
- 15) Can be performed at an outside facility
- 16) Induction Day 8, 15, 22 (Cycles 1-3), Day 15 (Cycle 4); consolidation Day 8, 15, 22 (Cycles 6-8), Day 15 (Cycle 9)
- 17) The following testing may be done if clinically indicated: Myeloma FISH, plasma cell proliferation, and flow cytometry (MRD).
- 18) Research blood and bone marrow collection per protocol IRB 521-93 will be done after consenting for 521-93 and according to that protocol. All processing will be done on Stabile 6.

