8.11 Instruction for initiation of a new cycle of therapy

A new cycle of treatment may begin on the scheduled Day 1 of a new cycle if:

- The ANC is $\geq 1.0 \times 10^9/L$ (=1000/microliter)
- The platelet count is $\geq 75 \times 10^9/L$ unless the participant has $\geq 50\%$ bone marrow infiltration in which case a platelet count of $\geq 50 \times 10^9/L$ is allowed
- Any other non-hematologic treatment -related adverse event that may have occurred has resolved to \leq Grade 1 or baseline severity.

If these conditions are not met on Day 1 of a new cycle, the subject will be evaluated weekly and a new cycle of therapy will be held until the toxicity has resolved as described below

If any drug dosing was halted during the previous cycle and was restarted with a one-level dose reduction without requiring an interruption for the remainder of the cycle, then that reduced dose level will be initiated on Day 1 of the new cycle.

If any drug dosing was omitted for the remainder of the previous cycle or if the new cycle is held due to known hematologic toxicity newly encountered on the scheduled Day 1, then the new cycle will be started with a one-level dose reduction. If a new cycle of therapy cannot be restarted within 4 weeks of the scheduled Day 1 due to non-resolution of drug related toxicities, the patient will be removed from protocol therapy and will go to event monitoring.

→ → Use the NCI Common Terminology Criteria for Adverse Events (CTCAE) version 4.0* unless otherwise specified ← ←

8.2 Dose modifications for ixazomib based on adverse events during a cycle (for each cycle during induction and consolidation and maintenance)

CTCAE System/Organ/Class (SOC)	ADVERSE EVENT	AGENT[#]	ACTION^{**}
Blood and lymphatic system disorders	Febrile neutropenia If platelet count $<30 \times 10^9/L$ or ANC $<1.0 \times 10^9/L$ or ANC $>1.0 \times 10^9/L$ (up to LLN) with fever (temperature $>38.5^\circ C$)	Ixazomib	Days 2-15: Ixazomib dose should be omitted. Complete blood count (CBC) with differential should be followed weekly. If ANC is $\geq 1.0 \times 10^9/L$ and/or platelet counts $\geq 30 \times 10^9/L$, ixazomib may be reinitiated with 1 dose level reduction (see Table 8.1). The subsequent cycle will use the reduced dose
Nervous System Disorders	Peripheral motor neuropathy OR Peripheral sensory neuropathy Newly developed Grade 1 with pain or \geq Grade 2	Ixazomib	Reduce dose of ixazomib to the next lower dose level

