8.3 Dose modifications for pomalidomide based on adverse events during a cycle

(For each cycle during induction and consolidation and maintenance)

Table 8.3			
CTCAE System/Organ/Class (SOC)	ADVERSE EVENT	AGENT	ACTION**
Investigations	Neutrophil count decreased If ANC $<1.0 \times 10^9/L$ or ANC $>1.0 \times 10^9/L$ (up to LLN) with fever (temperature $>38.5^\circ C$)	Pomalidomide	Omit pomalidomide dose. Follow CBC weekly. If neutropenia has resolved to \leq Grade 2 prior to Day 21 and fever has resolved, restart pomalidomide at next lower dose level and continue through Day 21 of a 28-day cycle. If febrile neutropenia is the only toxicity for which a dose reduction is required, G-CSF may be used and the pomalidomide dose maintained.
Investigations	Platelet count decreased If platelet count $<30 \times 10^9/L$	Pomalidomide	Omit pomalidomide dose Follow CBC weekly Hold anticoagulation/antiplatelet therapy until platelets $\geq 50,000/mm^3$ If platelet count resolves to \leq Grade 2 prior to Day 21, restart pomalidomide at next lower dose level and continue through Day 21 of each cycle
Skin and subcutaneous tissue disorders	Rash maculopapular Grade 2 or 3	Pomalidomide	Omit pomalidomide dose; follow weekly If the AE resolves to \leq Grade 1 prior to Day 21, restart pomalidomide at next lower dose level and continue through Day 21 of each cycle
	Grade 3-4 Stevens –Johnson Syndrome	Pomalidomide	Discontinue pomalidomide and remove patient from all study treatment
	\geq Grade 3 Erythema multiforme	Pomalidomide	Discontinue pomalidomide and remove patient from all study treatment

Table 8.3			
CTCAE System/Organ/Class (SOC)	ADVERSE EVENT	AGENT	ACTION**
	Erythroderma ≤Grade 3	Pomalidomide	Omit pomalidomide dose; follow weekly If the AE resolves to ≤Grade 1 prior to Day 21, restart pomalidomide at next lower dose level and continue through Day 21 of the 28-day cycle
	Rash, maculo-papular Rash, acneiform Grade 4	Pomalidomide	Discontinue pomalidomide and remove patient from all study treatment
Nervous system disorders	Peripheral sensory neuropathy Grade 3	Pomalidomide	Omit pomalidomide dose and follow at least weekly. If the AE resolves to ≤Grade 1 prior to Day 21, restart pomalidomide at next lower dose level and continue through Day 21 of the 28-day cycle
	Peripheral sensory neuropathy Grade 4	Pomalidomide	Discontinue pomalidomide and remove patient from all study treatment

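### The ±7-day window on the within-cycle CBCs equals their 7-day spacing, so compliant consecutive counts can be 20 days apart (21 on a looser reading) instead of 7

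*Combined protocol and SAP*

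**What the plan says.** Footnote 1 to the Section 4.1 test schedule gives scheduled on-therapy visits a common tolerance: they "will have a window of ± 7 days unless otherwise stated". The column headed for induction and consolidation carries footnotes 16 and 1, and the only test marked in it is the CBC with differential. Footnote 16 sets the days: "Induction Day 8, 15, 22 (Cycles 1-3), Day 15 (Cycle 4); consolidation Day 8, 15, 22 (Cycles 6-8), Day 15 (Cycle 9". Footnote 15 deals only with where the blood may be drawn. No narrower window for these counts appears anywhere. The End of Treatment column does carry its own window (±14 days), so the table sets a specific window where one is wanted.

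The counts drive dosing within the cycle:

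- **Ixazomib (Section 8.2 table).** If platelets or neutrophils are below the limits: "Days 2-15: Ixazomib dose should be omitted. Complete blood count (CBC) with differential should be followed weekly".
- **Pomalidomide (Table 8.3).** For a low neutrophil count: "Omit pomalidomide dose. Follow CBC weekly". If the count recovers before Day 21, the site is to "restart pomalidomide at next lower dose level and continue through Day 21 of a 28-day cycle".
- **Start of a cycle (Section 8.11).** "A new cycle of treatment may begin on the scheduled Day 1 of a new cycle if" the count thresholds listed there are met.

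Sections 9.9b and 9.9c refer back to the protocol's schedule and add further testing by usual practice, without dates.

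**The concern.** A schedule of counts a week apart only works if the tolerance is clearly shorter than a week. Here adjacent windows overlap, and a draw a full week late is not a deviation. The omission rules can act only on a count taken while drug is being given. The weekly follow-up in Tables 8.2 and 8.3 begins after a low count has been found, so it cannot close the gap before that finding.

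Low counts are expected. In the phase II study of pomalidomide 2 mg plus dexamethasone described in Section 1.5, 21 of 60 patients (35%) had grade 3/4 neutropenia, and "all first experienced the neutropenia in cycle 1-3; no new patients experienced grade 3/4 neutropenia in cycle 4 or later". A second study in that section saw more grade 4 neutropenia as the dose rose. This trial starts pomalidomide at 4 mg and adds ixazomib, and Section 8.0 asks for strict use of the modification table in the first two cycles. At stake is patient monitoring during early induction.

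**Working it through.** **Inputs.** Nominal days 8, 15 and 22 (footnote 16); window w = 7 days (footnote 1); 28-day cycle, so the next Day 1 is Day 29 (Section 7.1); ixazomib on Days 1, 8 and 15 and pomalidomide on Days 1-21 (Section 7.2). The plan states no gap figure to reproduce.

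**Permitted ranges at ±7.** Day 8 draw: Days 1-15. Day 15 draw: Days 8-22. Day 22 draw: Days 15-29.

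**Longest gap.** For adjacent nominal days d and d + 7, the largest compliant gap is (d + 7 + w) − (d − w) = 7 + 2w. At w = 7 this is 7 + 14 = 21 days (Day 1 to Day 22, or Day 8 to Day 29). If each draw must be separate from the Day 1 and Day 29 counts, the extremes are Day 2 to Day 22, or Day 8 to Day 28: 20 days.

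**Enumeration at ±7.** All whole-day schedules a < b < c were listed, with a, b and c in the three ranges and counts also on Days 1 and 29.

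- Separate draws (a ≥ 2, c ≤ 28): 1,933 schedules. A gap of 14 days or more occurs somewhere in the cycle in 574 (574/1,933 = 30%).
- Some of those gaps run into Days 22-28, when neither ixazomib nor pomalidomide is given. Cutting any open gap at Day 22 leaves 329 (329/1,933 = 17%).
- The Day 8 draw then lies on Days 2-15, so every schedule has at least one count in the period covered by the ixazomib omission rule. That count may be as early as Day 2: draws on Days 2, 22 and 23 comply and leave Days 3-21 without a count.

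**Narrower windows, separate draws.**

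| Window | Longest gap (days) | Schedules with a gap ≥ 14 days |
|---|---|---|
| ±7 | 20 | 574 of 1,933 |
| ±6 | 19 | 364 of 1,651 |
| ±5 | 17 | 160 of 1,111 |
| ±4 | 15 | 44 of 675 |
| ±3 | 13 | 0 of 343 |
| ±2 | 11 | 0 of 125 |
| ±1 | 9 | 0 of 27 |

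**Cycles 4 and 9 (single Day 15 draw).** At ±7 the draw may fall on Days 8-22, which is 15 days. Seven of these (Days 16-22) follow the last ixazomib dose and one (Day 22) follows the last pomalidomide dose. At ±3 the range is Days 12-18, which is 7 days. Three of these (Days 16-18) still follow the last ixazomib dose; none follows the last pomalidomide dose. The longest interval from Day 1 falls from 22 − 1 = 21 to 18 − 1 = 17 days, against 14 intended.

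**The case against.** The strongest reply is that the permitted extremes overstate the practical risk, and several parts of it stand.

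- **Off-drug time.** A reader might take the 30% as the share of schedules that leave two weeks of dosing unmonitored. It is not, because it includes gaps reaching into Days 22-28. The figure that matches the harm is 17%.
- **Some count always remains.** With separate draws no schedule lacks a count on Days 2-15. A reader might infer that a whole dosing period can pass with no count. That needs the Day 8 draw on Day 1 and the Day 15 draw on Day 22, which is 7 of 2,296 schedules when Days 1 and 29 are allowed. It is too remote a reading to carry the point.
- **The 14-day mark is not the protocol's.** It is a reviewer's yardstick. The protocol itself plans 14 days from Day 1 to Day 15 in Cycles 4 and 9, and only a pre-cycle count in maintenance.
- **The neutropenia evidence is limited.** It concerns Cycles 1-3 and came from daily dosing on Days 1-28. Consolidation uses pomalidomide 2 mg. Applying the 35% to this trial's patients would give an expected incidence, not a number of cytopenias missed because of the window.
- **The Day 1 count is partly inferred.** Section 8.11 sets thresholds for starting a cycle but not a draw date, the pre-treatment column also carries footnote 1, and footnote 7 lets baseline values serve for Cycle 1. The schedule counts depend on this assumption; the 7 + 2w result for adjacent draws does not.

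None of this supplies a narrower window. Sections 9.9b and 9.9c set no dates, and the weekly CBCs in Section 8 follow a low count rather than find it.

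**Conclusion.** The point holds as a weakness in safety monitoring that is cheap to correct. As written, the window equals the spacing in Cycles 1-3 and 6-8. Consecutive compliant counts can be 20 days apart (21 if a draw may coincide with Day 1 or Day 29) against 7 intended. Assuming separate draws and a count on each Day 1, 329 of 1,933 permitted schedules (17%) leave 14 days or more without a count within Days 1-22. The documents do not show how sites use the window, so this says nothing about how often such gaps would occur.

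The concern is greatest in Cycles 1-3 and weaker in consolidation. A reader might suspect an effect on the trial's conclusions, but the documents do not support that: PFS18 rests on progression and death, and the accrual-suspension rule in Section 16.42 counts only non-hematologic events.

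**What to change.** In footnote 1 of Section 4.1, exempt the within-cycle CBCs listed in footnote 16 from ±7 days and give them a window clearly shorter than their spacing, for example ±3 days or less. In the Day 8/15/22 cycles the longest gap becomes 13 days at ±3 or 11 at ±2. Keep ±7 days for other assessments.

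For the single draw in Cycles 4 and 9, ±3 keeps the count before the last pomalidomide dose but does not ensure that it precedes the last ixazomib dose. If that is wanted, the window must not extend past Day 15.

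The cost is one footnote edit in an amendment, tighter scheduling, and some more minor deviations for late draws. Footnote 15 already allows draws at an outside facility, which eases the burden.

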4.2 Event Monitoring/Survival Follow-up

	Event Monitoring Phase ¹				
	q. 3 months until PD	At PD	After PD q. 6 months	Death	New Primary
Event Monitoring	X	X	X	X	At each occurrence

1. If a patient is still alive 3 years after registration, no further follow-up is required.

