7.2 Treatment Schedule

	Doses and Schedule				
	Agent	Dose Level	Route	Day	Retreatment
Cycles 1-4 Induction (x 4 cycles)	Ixazomib	4 mg	PO	1, 8, 15	Every 28 days
	Pomalidomide	4 mg	PO	Days 1-21	Every 28 days
	Dexamethasone	40 mg	PO	1, 8, 15, 22	Every 28 days
Cycle 5 Transplantation ^{a,e,f}	Stem cell mobilization ^b followed by single ASCT				
Cycles 6-9 Consolidation ^c (x 4 cycles)	Ixazomib	4 mg	PO	1, 8, 15	Every 28 days
	Pomalidomide	2 mg	PO	Days 1-21	Every 28 days
	Dexamethasone	40 mg	PO	1, 8, 15, 22	Every 28 days
Cycles 10 and Beyond Maintenance (until progression or unacceptable toxicity) ^d	Ixazomib	4 mg	PO	1, 8, 15	Every 28 days

- SCT:** Can be performed per institutional practice. Stem cells collected and cryopreserved ahead of time or collected immediately prior to transplant can be used. Conditioning regimen preference left to the treating physician, but should not be enrolled in any additional therapy trials.
- If not previously collected and cryopreserved.
- If a patient previously has a dose reduction in induction, the consolidation phase will start and continue at reduced dose.
- Ixazomib maintenance would start at 4 mg unless dose has been previously reduced in the Induction or consolidation phase due to a non-hematologic toxicity specifically attributed to Ixazomib.
- Window period is 2-4 weeks between Induction and ASCT; 60-120 days between ASCT and Consolidation and 0-4 weeks between the Consolidation and Maintenance phases.
- Melphalan conditioning followed by stem cell infusion is being considered as 'cycle 5' for logistical reasons only. No additional toxicity data will be collected in the immediate post ASCT period until day 60-100 when the patient returns for routine post ASCT-reevaluation.

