7.6 Treatment at enrolling institution

For this protocol, the patient must return to the consenting institution for evaluation at least every 28 days. Treatment by a local medical doctor (LMD) is not allowed.

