13.0 Treatment/Follow-up Decision at Evaluation of Patient

- 13.1 Patients who are MRD negative, sCR, CR, VGPR, PR, or SD (or usCR, uCR, uVGPR, uPR) will continue treatment per protocol.
- 13.2 Patients who develop progressive disease while receiving therapy will go to the event-monitoring phase.
- 13.3 Patients who go off protocol treatment for reasons other than PD will go to the event-monitoring phase per Section 18.0.
- 13.4 Criteria for Discontinuation of Treatment
Patients may discontinue treatment for the following reasons:
- Progressive multiple myeloma
 - Patient refuses further treatment on the trial
 - Patient develops an intercurrent illness that precludes further participation, or requires a prohibited concomitant treatment
 - The Investigator withdraws the patient in the patient's best interests
 - Patient is lost to follow-up (defined as the inability to contact the patient on 3 separate occasions)
 - Administrative reasons (e.g., the patient is transferred to hospice care)
 - An adverse event, which in the opinion of the Investigator, precludes further trial participation
- All attempts should be made to complete the End of Study procedures when the patient discontinues treatment. Patients should go to event monitoring per Section 18.0, unless the patient refuses further study participation or is lost to follow-up.
- 13.5 Criteria for Study Discontinuation
The study may be temporarily or permanently discontinued at any site and at any time. Reasons for study discontinuation may include, but are not limited to, the following:
- Safety concerns

- Poor enrollment
- Non-compliance with the protocol, Good Clinical Practice guidance or other regulatory requirements by the Investigator(s)
- Request to discontinue the trial by a regulatory or health authority or an IRB
- Manufacturing difficulties/concerns

All Investigators and the requisite regulatory authorities will be notified if the study is suspended or terminated for safety reasons. In the case of such termination, the Investigator will notify the IRB.

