16.32 Secondary Outcome Analyses

- 16.321 The overall response rate will be estimated by the number of patients who achieve a sCR, CR, VGPR, or PR divided by the total number of evaluable patients. All evaluable patients will be used for this analysis. Exact binomial 95% confidence intervals for the true overall response rate will be calculated.
- 16.322 The \geq VGPR response rate will be estimated by the number of patients who achieve a sCR, CR, or VGPR divided by the total number of evaluable patients. All evaluable patients will be used for this analysis. Exact binomial 95% confidence intervals for the true overall \geq VGPR response rate will be calculated.
- 16.323 Overall survival is defined as the time from registration to the last date of documentation of follow-up or death due to any cause. The distribution of overall survival will be estimated using the method of Kaplan-Meier (Kaplan, E. and Meier, P., 1958)
- 16.322 Adverse Events: All eligible patients that have initiated treatment will be considered evaluable for assessing adverse event rate(s). The maximum grade for each type of adverse event will be recorded for each patient, and frequency tables will be reviewed to determine patterns. Additionally, the relationship of the adverse event(s) to the study treatment will be taken into consideration.

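### Required survival follow-up stops at 3 years for patients in event monitoring but not for patients on maintenance, so Kaplan-Meier overall survival is biased upward after month 36

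*Combined protocol and SAP*

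**What the plan says.** - **Section 4.2** sets the event-monitoring schedule, with survival contact "After PD q. 6 months". Footnote 1, whose marker sits on the Event Monitoring Phase header, says: "If a patient is still alive 3 years after registration, no further follow-up is required".
- **Section 7.2** gives ixazomib maintenance "until progression or unacceptable toxicity", with no limit in time. **Section 7.6** adds that "the patient must return to the consenting institution for evaluation at least every 28 days", so vital status is known for as long as treatment lasts.
- **Section 13.2** covers progression: "Patients who develop progressive disease while receiving therapy will go to the event-monitoring phase". **Section 13.3** covers every other reason for stopping: "Patients who go off protocol treatment for reasons other than PD will go to the event-monitoring phase per Section 18.0".
- **Section 16.323** gives the endpoint: "Overall survival is defined as the time from registration to the last date of documentation of follow-up or death due to any cause". Kaplan-Meier is the estimator. No truncation time, common cut-off or landmark is given.
- **Sections 10.52 and 10.623** require reporting of any death within 30 days of the last dose, and of later deaths judged at least possibly related to treatment. Neither carries a 3-year limit.

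**The concern.** Up to month 36 every patient, on or off treatment, is under required survival follow-up. After month 36 that holds only for patients still on maintenance, who by definition have neither progressed nor stopped. Each of them leaves the required follow-up soon after progressing or stopping.

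Kaplan-Meier assumes that a censored patient has the same future risk of death as those who remain at risk. Here the patients censored after month 36 have mostly just progressed and are at higher risk. The dependence is created by the follow-up rule and is not chance loss.

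Overall survival from study entry is a named secondary goal (2.22), and 16.5 commits secondary endpoints to public reporting. A curve that flattens after month 36 in a single-arm trial with open-ended maintenance could be read as a plateau due to maintenance, with no control arm to expose the artefact.

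**Working it through.** **Plan figures.** The documents state no overall survival figure to reproduce. The figures they do state, for the rule of at least 14 successes in 21, reproduce by exact binomial: P(X ≥ 14) = 0.0946 at p = 0.50 (printed 0.095) and 0.8701 at p = 0.75 (printed 0.870). They concern PFS18 and do not depend on follow-up after month 36.

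**Who is at risk after month 36 under required follow-up**

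| Status | Follow-up required until |
|---|---|
| Off treatment before month 36, alive | month 36 (4.2, footnote 1) |
| On maintenance at month 36 | leaving treatment (7.2, 7.6), plus 30 days for deaths (10.52, 10.623) |
| Leaves maintenance after month 36 | nothing further, except treatment-related deaths |

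**Worked example.** From the documents: PFS18 = 50%, the null value in 16.21. Assumed: exponential PFS; 10% of PFS events are deaths without progression; median survival after progression 24 months. The 30-day rule is left out here and added below.

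With h = ln 2/18 and m = ln 2/24, the factor 0.9·h/(h − m) equals 0.9 × 4 = 3.6, so true survival is

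OS(t) = 2^(−t/18) + 3.6 × [2^(−t/24) − 2^(−t/18)].

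- OS(36) = 0.2500 + 3.6 × (0.3536 − 0.2500) = 0.623
- OS(48) = 0.1575 + 3.6 × (0.2500 − 0.1575) = 0.491
- OS(60) = 0.0992 + 3.6 × (0.1768 − 0.0992) = 0.378

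After month 36 the only deaths seen are those without progression, at rate 0.1h, so the large-sample Kaplan-Meier value is OS(36) × 2^(−(t − 36)/180):

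- month 48: 0.623 × 0.9548 = 0.595, which is 10.4 points too high
- month 60: 0.623 × 0.9117 = 0.568, which is 18.9 points too high

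With PFS18 = 75% and the rest unchanged, simulation gives 70.3% true against 78.0% at month 48, and 61.3% against 76.5% at month 60.

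**Range over assumptions.** Illness-death simulations were run with PFS18 of 50% or 75%.

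- Set A: median post-progression survival 12, 24 or 36 months; 10% or 30% of PFS events are deaths without progression; 0% or 30% stop treatment without progression before month 36.
- Set B: median post-progression survival 18, 24 or 36 months; death without progression 0.002 per month; toxicity stop 0.005 or 0.015 per month.

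Upward bias in percentage points:

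| Month | Set A | Set A, 30-day deaths counted | Set B | Set B, 30-day deaths counted |
|---|---|---|---|---|
| 36 | 0 | 0 | 0 | 0 |
| 42 | 1.5 to 7 | 1.5 to 6 | 3 to 7 | 3 to 6.5 |
| 48 | 3 to 12.5 | 3 to 11.5 | 6 to 13 | 5 to 12 |
| 60 | 5 to 21 | 5 to 19 | 11.5 to 24 | 11 to 22 |

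The direction was upward in every scenario. In set B, 25 × 0.25 × exp(−36 × 0.015) = 3.6 to 25 × 0.5625 × exp(−36 × 0.005) = 11.7 patients are still on treatment at month 36. With no toxicity stops at all the upper figure would be 25 × 0.5625 = 14.1.

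Against a binomial standard error at n = 25, the month-48 bias in set B runs from 0.057/√(0.81 × 0.19/25) = 0.7 to 0.132/√(0.565 × 0.435/25) = 1.3 standard errors. With PFS18 of 50% and a post-progression median of 18 months, the true median is about 42 months, yet the curve without the 30-day deaths is still at 0.55 at month 60, so the median would be reported as not reached.

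**Timing.** The first report is due when the last patient has 18 months of follow-up (16.23, 16.3).

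- At 2 patients per month, accrual takes 25/2 = 12.5 months. The report falls at 12.5 + 18 = 30.5 months, and nobody is past month 36.
- With the stated two-year enrolment it falls at 24 + 18 = 42 months. Then 25 × 6/24 ≈ 6 patients could be past month 36, of whom about 6 × 4/25 ≈ 1 to 6 × 12/25 ≈ 3 would be on treatment.

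**The case against.** **Deaths after progression are not all lost.** A reader might infer that no post-progression death can enter the curve beyond month 36. Sections 10.52 and 10.623 rule that out: deaths within 30 days of the last dose, and later related deaths, must be reported. This stands as a correction, but counting the 30-day deaths lowers the month-48 bias only by about a point or less.

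**The footnote sets a minimum.** It says what is required and does not forbid more. Section 10.8 also asks for new primary malignancies for at least three years after the last dose, which implies some contact past month 36. That weakens any claim that the bias is certain. It does not amount to planned survival collection, and uneven voluntary recording would not make the censoring uninformative.

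**The footnote may be meant for everyone.** The title of 4.2 mentions survival follow-up, the footnote speaks of a patient without qualification, and 18.1 and 18.2 point to a data submission schedule that is not in the documents. A common 3-year limit is a possible reading. The marker's place on the Event Monitoring Phase and the open-ended maintenance visits speak against it, and 16.323 does not state it.

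**No planned result depends on the tail.** The documents name no 4-year or 5-year survival and no median. This stands, and it confines the point to later updates.

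**Truncation discards recorded deaths.** True. Following everyone for death to a common cut-off would also remove the bias, but it needs data that the protocol does not now require.

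**Conclusion.** The point holds in limited form. As written, 4.2, 7.2, 13.2, 13.3 and 16.323 together give informative censoring of overall survival after month 36, with upward bias.

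The size is roughly 3 to 13 points at month 48, in a tail of about 4 to 12 of 25 patients. It depends on assumed post-progression survival, death without progression, toxicity stops and a data cut late enough to have patients that far out. None of these is in the documents.

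A reader might go further and doubt the trial's main result or its first report. The documents do not support that. PFS18, the rule of 14 in 21, its significance level and power, and overall survival up to month 36 are untouched. At the first planned report the effect is nil or slight.

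Confidence is moderate, because footnote 1 sets a minimum and admits the reading of a common 3-year limit. The change is worth making under either reading.

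**What to change.** Add to 16.323, citing 4.2 footnote 1 as the reason: *For the Kaplan-Meier estimate of overall survival, every patient alive at 36 months from registration, on or off treatment, is administratively censored at 36 months. Overall survival is reported to 36 months only, and a median is given only if it is reached by then.*

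This removes the bias. If footnote 1 was meant as a limit for all patients, the same sentence brings 16.323 into line with it.

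The cost is one sentence of analysis wording, with no new data, visits or patients and no change to treatment. The downside is that deaths and survival time recorded after month 36 do not enter this estimate. They can be listed descriptively, with each patient's treatment status.
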